## 19. DATA COLLECTION, RETENTION, AND MONITORING

### 19.1. Data Collection Instruments

The clinician will prepare and maintain adequate and accurate source documents designed to record all observations and other pertinent data for each subject treated with the investigational drug. Case report forms will be used to collect study data.

Study personnel at each site will enter data from source documents corresponding to a subject's visit into the CRF when the information corresponding to that visit is available. Patients will not be identified by name in the study database or on any study documents to be collected by the sponsor (or designee), but will be identified by a site number and subject identification number.

If a correction is required in the CRF, it should be made by a using a single line to strike out any text. The staff member making the correction should initial and date the correction. All corrections in study-related documents must follow ALCOA (ie, attributable, legible, contemporaneous, original, accurate) data integrity principals.

The clinician is responsible for all information collected on subjects enrolled in this study. All data collected during the course of this study must be reviewed and verified for completeness and accuracy by the clinician.

## 19.2. Data Management Procedures

The data will be entered into the subject's medical records/source documents and CRFs. The sponsor or designee will be responsible for data processing, in accordance with procedural documentation.

All procedures for the handling and analysis of data will be conducted using good computing practices meeting ICH and EU guidelines for the handling and analysis of data for clinical trials.

# 19.3. Availability and Retention of Study Records

The clinician must make study data accessible to the monitor, other authorized representatives of the sponsor (or designee), IRB, and regulatory agency inspectors upon request. A file for each subject must be maintained that includes the signed ICF, confidentiality commitments, assent form, and copies of all source documentation related to that subject. The clinician must ensure the reliability and availability of source documents from which the information in the CRF was derived.

All study documents (subject files, signed ICFs, copies of CRFs, etc.) must be kept secured for a period of 2 years following marketing of the investigational product or for 2 years after sites have been notified that the Investigational New Drug application has been discontinued. There may be other circumstances for which the sponsor is required to maintain study records and, therefore, the sponsor should be contacted prior to removing study records for any reason.

# 19.4. Monitoring

Monitoring of data will be conducted by the sponsor or designee according to ICH Guidelines for GCP (E6). By signing this protocol, the clinician grants permission to the sponsor (or

designee) and appropriate regulatory authorities to conduct on-site monitoring and/or auditing of all appropriate study documentation.

# 19.5. Patient Confidentiality

In order to maintain subject confidentiality, only a site number and subject identification number will identify all study subjects on documentation submitted to the sponsor. Additional subject confidentiality issues (if applicable) are covered in the Study Agreement.

# 20. ADMINISTRATIVE, ETHICAL, AND REGULATORY CONSIDERATIONS

The study will be conducted according to the Declaration of Helsinki, IRB requirements, and local regulations.

To maintain confidentiality, all laboratory specimens, CRFs, reports, and other records will be identified by a coded number. All study records will be kept in a locked file cabinet and code sheets linking a subject's name to a subject identification number will be stored separately in another locked file cabinet. Clinical information will not be released without written permission of the subject, except as necessary for monitoring by the applicable regulatory authority. The clinician must also comply with all applicable privacy regulations (eg, Health Insurance Portability and Accountability Act of 1996, European Union Data Protection Directive 95/46/EC).

## **20.1.** Protocol Amendments

Any amendment to the study protocol will be written by the sponsor. Protocol amendments cannot be implemented without prior written IRB approval except as necessary to eliminate immediate safety hazards to subjects. A study amendment intended to eliminate an apparent immediate hazard to subjects may be implemented immediately, provided the IRBs are notified as soon as possible.

### 20.2. Institutional Review Boards

The protocol and consent form will be reviewed and approved by the IRB of each participating site prior to study initiation. Serious adverse events regardless of causality will be reported to the IRB in accordance with the standard operating procedures and policies of the IRB, and the clinician will keep the IRB informed as to the progress of the study. The clinician will obtain assurance of IRB compliance with regulations.

Any documents that the IRB may need to fulfill its responsibilities (such as protocol, protocol amendments, Investigator's Brochure, consent forms, information concerning subject recruitment, payment or compensation procedures, or other pertinent information) will be submitted to the IRB. The IRB's written unconditional approval of the study and the ICF will be in the possession of the clinician before the study is initiated. The IRB's unconditional approval statement will be transmitted by the clinician to the sponsor or designee prior to the shipment of study supplies to the site. This approval must refer to the study by exact protocol title and number and should identify the documents reviewed and the date of review.

Study and/or informed consent modifications or changes may not be initiated without prior written IRB approval except when necessary to eliminate immediate hazards to the subjects or when the change(s) involves only logistical or administrative aspects of the study. Such modifications will be submitted to the IRB and written verification that the modification was submitted and subsequently approved should be obtained.

The IRB must be informed of revisions to other documents originally submitted for review; serious and/or unexpected adverse events occurring during the study in accordance with the standard operating procedures and policies of the IRB; new information that may affect

adversely the safety of the subjects or the conduct of the study; an annual update and/or request for re-approval; and when the study has been completed.

### 20.3. Informed Consent Form

Informed consent will be obtained in accordance with the Declaration of Helsinki, ICH GCP, and local regulations.

The informed consent document will contain the elements required by the ICH and will also comply with 21 CFR Part 50. The clinician will send an IRB-approved copy of the ICF to the sponsor (or designee) for the study file.

A properly executed, written ICF will be obtained from each subject prior to entering the subject into the study. Information should be given in both oral and written form and subjects (or their legal representatives) must be given ample opportunity to inquire about details of the study. If appropriate and required by the IRB, assent from the subject will also be obtained. If a subject is unable to sign the ICF and privacy authorization (if applicable), a legal representative may sign for the subject. A copy of the signed ICF (and assent) will be given to the subject or legal representative of the subject and the original will be maintained with the subject's records.

Separate consent (on the same ICF) will be obtained from subjects providing blood samples to use for research on plasma bile acid biomarkers.

### 20.4. Publications

The sponsor's decision to publish or otherwise publicly communicate the results of this study will be made in accordance with all applicable laws, regulations, and sponsor policies regarding publication and communication of clinical study results.

Terms and provisions of the investigator's publication rights are governed by the Publication Section in the Clinical Trial Agreement.

# **20.5.** Clinician Responsibilities

By signing the Agreement of Clinician form, the clinician agrees to:

- 1. Conduct the study in accordance with the protocol and make changes only after notifying the sponsor (or designee), except when to protect the safety, rights, or welfare of subjects.
- 2. Personally conduct or supervise the study.
- 3. Ensure that the requirements relating to obtaining informed consent and IRB review and approval meet federal guidelines, as stated in 21 CFR, Parts 50 and 56.
- 4. Report to the sponsor or designee any AEs that occur in the course of the study, in accordance with 21 CFR 312.64.
- 5. Ensure that all associates, colleagues, and employees assisting in the conduct of the study are informed about their obligations in meeting the above commitments.
- 6. Maintain adequate and accurate records in accordance with 21 CFR 312.62 and make those records available for inspection with the sponsor (or designee).

- 7. Ensure that an IRB that complies with the requirements of 21 CFR Part 56 will be responsible for initial and continuing review and approval of the study.
- 8. Promptly report to the IRB and the sponsor (or designee) all changes in the research activity and all unanticipated problems involving risks to subjects or others (to include amendments and required safety reports).
- 9. Seek IRB approval before any changes are made in the study, except when necessary to eliminate hazards to the subjects.
- 10. Comply with all other requirements regarding the obligations of clinical investigators and all other pertinent requirements listed in 21 CFR Part 312.

## 22. SCHEDULE OF ASSESSMENTS AND PROCEDURES

Table 4: Schedule of Assessments and Procedures – Screening through Week 26

Visit Number		1	2-13	14
Day	–45 through –1	1	15 – 169	183
Window (weeks)			(± 1)	(± 1)
Time Point or Frequency	Screening	1st Dose a	Every 2 weeks (Weeks 2 – 24)	Week 26
Procedure				
Informed consent	X			
Confirm patient eligibility	X	X		
Demographics	X			
Medical history b	X			
Clinician-CGIC assessment c	X			X
NPC-SS Intake c	X			X
EQ-5D-3L assessment c	X			X
Height	X			
Weight	X	X	X	X
Vital signs d,e	X	X f	X f	$\chi^{\mathrm{f}}$
Physical examination g	X			X
Urinalysis	X			X
Serum pregnancy test	X			
Urine pregnancy test				X
12-lead ECG	X			
Neurological examination h	X			X
Audiologic testing i	X			X
Diagnostic threshold auditory brainstem response j	X			

Visit Number		1	2-13	14
Day	–45 through –1	1	15 – 169	183
Window (weeks)			(± 1)	(± 1)
Time Point or Frequency	Screening	1st Dose a	Every 2 weeks (Weeks 2 – 24)	Week 26
Procedure				
Blood for clinical laboratory tests k	X			X
Blood for plasma bile acids 	X			X
LP and adrabetadex administration m		X	X	X
CSF for routine CSF analysis n		X		
Adverse events e	X	X	X	X
Prior and concomitant medications/therapies e	Χ°	X	X	X

<sup>a Patients who are already receiving adrabetadex may be screened and enrolled (receive first dose) on the same day.

Only collected for subjects unable to provide reliable behavioral PTA results. For these subjects, Diagnostic ABR will be collected at Screening, within 72 hours prior to dose escalation and within 72 hours prior to the visit subsequent to dose escalation, once every 2 months after a clinically significant change in hearing is observed until hearing is reported to be stable, and once per year when hearing is otherwise thought to be stable. For subjects who are unable to provide reliable behavioral PTA results at the 6-month interval, this evaluation will not be performed.

<sup>b Medical history includes history of NPC, diagnosis date, and prior NPC treatments.

<sup>c The efficacy assessments (Clinician-CGIC, NPC-SS, and EQ-5D-3L) should be performed *prior to other assessments and procedures*. In addition, the Clinician-CGIC should be conducted prior to other efficacy assessments.

<sup>d Vital signs (blood pressure, pulse rate, respirations, and body temperature) will be recorded following a 5-minute rest in supine position.

<sup>e The collection period of adverse events, and concomitant medications will begin after informed consent is obtained and end at Follow-up Visit 3; the collection of vital signs will begin after informed consent is obtained and end at Follow-up Visit 1 (see Table 6).

<sup>f A second set of vital signs will be recorded following recovery from LP.

g Complete physical examination at Screening; abbreviated physical examination at all other visits.

<sup>h Complete neurological examination at Screening; abbreviated neurological examination at Week 26. A complete neurological examination will be conducted at End of Study/ Early Termination.

Audiologic evaluations will also be performed prior to each dose escalation (within 72 hours prior with results available at the study visit), within 72 hours prior to the subsequent visit following a dose escalation (with results available at the study visit) per Section 7.2, at 1-month intervals following a change in hearing until stable hearing is confirmed; and when indicated by a subjective hearing impairment AE of CTCAE grade 3 or higher, or at the discretion of the investigator for subjective hearing impairment AE of CTCAE grade < 3 (Section 14.1.8) Hearing impairment AE evaluation will be performed as described in Section 12.2.6.1.

Visit Number		1	2-13	14
Day	−45 through −1	1	15 – 169	183
Window (weeks)			(± 1)	(± 1)
Time Point or Frequency	Screening	1st Dose a	Every 2 weeks (Weeks 2 – 24)	Week 26
Procedure				

<sup>k Clinical laboratory blood tests include chemistry, hematology, and coagulation.

CGIC = Clinical Global Impression of Change; CSF = cerebrospinal fluid; ECG = electrocardiogram; LP = lumbar puncture; NPC = Niemann-Pick type C disease; NPC-SS = Niemann-Pick Type C Disease Severity Scale

<sup>1 Only for subjects who provide separate consent for this assessment.

<sup>m Prior to each dose escalation, an audiology examination should be performed (within 72 hours) to assess for hearing impairment. If hearing impairment is observed, dose escalation should not proceed. An audiology examination should also be performed within 72 hours prior to the subsequent visit following a dose escalation (with results available at the study visit) to see if the subject can continue at the same dose.

<sup>n Collected from treatment-naïve subjects only. Red blood cell count, white blood cell count, white blood cell differential, glucose, and protein.

<sup>o Any medications used to treat NPC in the past (no time limit) and any other medications taken within 30 days of the Screening Visit will be recorded at the Screening Visit.

Table 5: Schedule of Assessments and Procedures – Week 28 and Thereafter, Including End of Study/Early Termination

Window (weeks)	(± 1)	(± 1)	(± 1)	(+1)
Frequency (starting at Week 28) or Time Point	Every 2 Weeks After 1st Dose (Weeks 28, 30, 32, etc.)	Every 6 Months After 1st Dose (Weeks 52, 78, 104, 130, 156, 182, etc.)	Additional Assessment Every 12 Months After 1st Dose (Weeks 52, 104, 156, 208, etc.)	End of Study/ Early Termination
Procedure				
Clinician-CGIC assessment a		_b		
NPC-SS Intake a		_b		
EQ-5D-3L assessment a		_b		
Weight	X	X		X
Vital signs c,b,d	X e	X e		
Abbreviated physical examination		X		X
Urinalysis		X		X
Urine pregnancy test		X		X
Neurological examination f		X		X
Audiologic testing g		X		X
Diagnostic threshold auditory brainstem response h		_h	-h	_h
Blood for clinical laboratory tests i,i		X		X
Blood for plasma bile acids k,j		_b		
LP and adrabetadex administration k	X	X		
Adverse events d	X	X		X

Window (weeks)	(± 1)	(± 1)	(± 1)	(+1)
Frequency (starting at Week 28) or Time Point	Every 2 Weeks After 1st Dose (Weeks 28, 30, 32, etc.)	Every 6 Months After 1st Dose (Weeks 52, 78, 104, 130, 156, 182, etc.)	Additional Assessment Every 12 Months After 1st Dose (Weeks 52, 104, 156, 208, etc.)	End of Study/ Early Termination
Procedure				
Concomitant medications/therapies d	X	X		X

All subjects who discontinue protocol treatment will be requested to return to the clinic to complete an Early Termination Visit.

Note: Any assessment done every 6 months is, by definition, done every 12 months.

- a The efficacy assessments (Clinician-CGIC, NPC-SS, and EQ-5D-3L) should be performed *prior to other assessments and procedures*. In addition, the Clinician-CGIC should be conducted prior to other efficacy assessments.
- b Procedure(s) should not be performed starting when the protocol amendment is approved by the respective IRB/Ethics Committee.
- c Vital signs (blood pressure, pulse rate, respirations, and body temperature) will be recorded following a 5-minute rest in supine position.
- d The collection period of adverse events, and concomitant medications will begin after informed consent is obtained (see Table 4) and end at Follow-up Visit 3; the collection of vital signs will begin after informed consent is obtained and end at Follow-up Visit 1 (see Table 6).
- e A second set of vital signs will be recorded following recovery from LP.
- f Complete neurological examination every 12 months after first dose (starting at Week 52 in this table) and abbreviated neurological examination every 6 months in between. A complete neurological examination will be conducted at End of Study/Early Termination.
- g Audiologic evaluations will also be performed prior to each dose escalation (within 72 hours prior with results available at the study visit), within 72 hours prior to the subsequent visit following a dose escalation (with results available at the study visit) per Section 7.2, at 1-month intervals following a change in hearing until stable hearing is confirmed; and when indicated by a subjective hearing impairment AE of CTCAE grade 3 or higher, or at the discretion of the investigator for subjective hearing impairment AE of CTCAE grade < 3 (Section 14.1.8). Hearing impairment AE evaluation will be performed as described in Section 12.2.6.1.
- h Do not perform starting 20 January 2021 (implemented in advance of amendment 2 as there is a direct impact to subject safety).
- i Clinical laboratory blood tests include chemistry, hematology, and coagulation.
- j Only for subjects who provide separate consent for this assessment.
- k Before each dose escalation, an audiology examination should be performed (within 72 hours) to assess for hearing impairment. If hearing impairment is observed, dose escalation should not proceed. An audiology examination should also be performed within 72 hours prior to the subsequent visit following a dose escalation (with results available at the study visit) to see if the subject can continue at the same dose.

CGIC = Clinical Global Impression of Change; ECG = electrocardiogram; LP = lumbar puncture; NPC-SS = Niemann-Pick Type C Disease Severity Scale

**Table 6:** Follow-up Visit

Window (weeks)	(± 1)
Procedure	Follow-up Visit a (2 weeks after EOS/ET visit)
Complete physical examination	X
Vital signs b	X
Urine pregnancy test	X
Audiologic testing c	X
Adverse events	X
Concomitant medications/therapies	X

<sup>a Follow-up visits not required for subjects who transition to another sponsor study.

b Vital signs (blood pressure, pulse rate, respirations, and body temperature) will be recorded following a 5-minute rest in supine position.

<sup>c Diagnostic ABR testing will not be performed after 20 January 2021.

EOS = End of Study; ET = Early Termination

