# 12.2.6. Audiologic Evaluation

Acoustic reflexes, pure tone audiometry (PTA), and auditory brainstem responses (ABRs) have been used to date to evaluate abnormalities that have been previously reported in NPC subjects (King 2014). As of 20 January 2021, ABRs will not be collected, as the potential risks with the procedure outweigh the potential benefit of the data.

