#### 12.2.6.1. Audiologic Testing

Audiologic evaluations will be performed at the time points specified in Table 4.

Audiologic assessments will include:

- Evaluation of middle ear function (tympanometry).
- Air conduction PTA.
- Speech reception threshold.

• Bone conduction PTA (only at Screening and when a clinically significant change in hearing is observed in air conduction PTA).

A clinically significant change is defined as:

- ≥20 dB increase at any one test frequency relative to baseline measure.
- ≥10 dB increase at any two adjacent test frequencies relative to baseline measure.
- Loss of response at three consecutive test frequencies where responses were previously obtained (specifically the highest frequencies tested) on baseline measure.

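### Table 4 still schedules auditory brainstem response testing with no stop date, while Section 12.2.6 and Tables 5 and 6 stop it from 20 January 2021

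*Combined protocol and SAP*

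**What the plan says.** Section 12.2.6 ends ABR testing and gives the reason: "As of 20 January 2021, ABRs will not be collected, as the potential risks with the procedure outweigh the potential benefit of the data". The Table 5 ABR footnote agrees: "Do not perform starting 20 January 2021". It adds that the stop was put in place ahead of Amendment 2 because it bears directly on subject safety. A Table 6 footnote also excludes ABR after that date.

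Table 4, which covers Screening through Week 26, has no such statement. Its row "Diagnostic threshold auditory brainstem response j" keeps a mark at Screening. The footnote, which concerns subjects without reliable behavioral PTA, reads "For these subjects, Diagnostic ABR will be collected at Screening, within 72 hours prior to dose escalation" and goes on to the visit after escalation. It then adds two recurring triggers. One follows a hearing change: "once every 2 months after a clinically significant change in hearing is observed until hearing is reported to be stable". The other is a routine annual test: "once per year when hearing is otherwise thought to be stable". The footnote's closing sentence is: "For subjects who are unable to provide reliable behavioral PTA results at the 6-month interval, this evaluation will not be performed".

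On where to find the timing, Section 12.2.6.1 says: "Audiologic evaluations will be performed at the time points specified in Table 4". Section 13 also names Table 4 alone. Section 12, however, refers to Section 22 as a whole, and Section 15.1 refers to Table 5 for the End of Study visit.

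**The concern.** The protocol gives two instructions on one procedure, and both are current text. Neither is a leftover in an amendment summary. The table without the stop is also the one that Sections 12.2.6.1 and 13 name.

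In a subject who triggers the Table 4 footnote, performing ABR departs from Section 12.2.6, and omitting it departs from the footnote. Section 16 counts a failure to follow a specified procedure as a major deviation when it is judged to put subjects at increased risk, so sites need one instruction. The sponsor acted on ABR early for safety reasons, which makes the loose end worth closing even if few subjects are touched.

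**Working it through.** The plan has no figure to reproduce. The check compares the passages and then uses dates to see whether Table 4 could still govern anyone.

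**Step 1: where the stop appears**

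| Place | ABR instruction | Stop stated? |
|---|---|---|
| Section 12.2.6 | Not collected as of 20 January 2021 | Yes |
| Table 4 row and footnote | Screening, escalation, 2-monthly, yearly | No |
| Table 5 footnote (Week 28 onward, and End of Study) | Not performed starting 20 January 2021 | Yes |
| Table 6 footnote (follow-up) | Not performed after 20 January 2021 | Yes |

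Table 4 also keeps plain Week 26 marks for the two efficacy scales and the quality-of-life questionnaire, which Section 12.3 says will not be collected. This suggests, without proving it, that Table 4 was not updated with the rest.

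**Step 2: which Table 4 triggers are still live**

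- *Screening:* enrolment closed on 20 January 2021 (Section 9). Closed.
- *Dose escalation:* increases are barred from 21 April 2021 (Synopsis, Dose Adjustment). Closed.
- *Yearly:* the 12-month time points (Weeks 52, 104 and so on) are in Table 5, which forbids ABR. Counting from a Screening ABR at the earliest allowed day changes nothing: 45 + 182 + 7 = 234 days to the end of the Week 26 window, short of 365. Closed in practice.
- *2-monthly after a clinically significant hearing change:* nothing outside Section 12.2.6 closes this for a subject still at or before Week 26. Open.

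**Step 3: could a subject still be at or before Week 26?**

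Inputs: Week 26 is Day 183, so Day 1 + 182 days, with a window of ± 1 week (Table 4). The protocol date is 23 June 2021 (Synopsis). The documents give no subject's first-dose date, so the latest Day 1 is an assumption, shown as a range.

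- *Latest Day 1 on 20 January 2021:* 20 January + 182 days = 21 July 2021, and + 7 days = 28 July 2021. These are 28 and 35 days after the protocol date.
- *Latest Day 1 on 6 March 2021:* this takes a subject screened on 20 January and dosed at the end of the 45-day screening period, and supposes that this was allowed after enrolment closed. 6 March + 182 days = 4 September 2021, and + 7 days = 11 September 2021. These are 73 and 80 days after the protocol date.
- *Earliest Day 1 still inside Table 4 on the protocol date:* 23 June 2021 − 182 days = 23 December 2020, or 16 December 2020 with the window.

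**Step 4: how many tests per subject**

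Take 2 months as about 61 days. In the first case at most one 2-monthly test could fall due under this version, because 35 < 61. In the second case at most two could, because 80 is between 61 and 122.

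**The case against.** The best reply is that a careful site would not go wrong. The stop and its reason come directly before Section 12.2.6.1. That section's assessment list omits ABR, and Table 4 keeps audiologic testing and ABR in separate rows, so the pointer to Table 4 does not itself call for ABR. Most triggers are closed elsewhere. All this stands, and it limits the weight of the point. It does not put the stop into Table 4 or switch off the 2-monthly trigger there.

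A reader might infer more than the text supports, in four ways:

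- *That Table 4 is the only schedule sites are sent to.* This is true of Sections 12.2.6.1 and 13, but Section 12 cites all of Section 22 and Section 15.1 cites Table 5.
- *That the footnote contradicts itself,* by testing only subjects without reliable PTA and then excluding those same subjects. The closing sentence is limited to the 6-month interval, which fits the blank Week 26 cell. It is ambiguous about which evaluation it means, but it is not a self-contradiction.
- *That the recurring triggers reach any subject at any time.* From Week 28, Table 5 gives an explicit contrary instruction.
- *That hearing data will differ across sites.* This is not shown. ABR is outside the current assessment list, and Section 18 plans only descriptive summaries of audiologic change by visit.

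**Conclusion.** The point holds as a conflict between current passages. The Table 4 row and footnote schedule ABR without an end date, while Section 12.2.6 and Tables 5 and 6 end it from 20 January 2021 on risk and safety grounds.

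What remains open is mainly the 2-monthly trigger, for a subject who is at or before Week 26, lacks reliable behavioral PTA, and has had a clinically significant hearing change. Whether anyone meets all three conditions is unknown and the number may be zero. The dates show only that it was possible: with a last first dose on 20 January 2021, the Table 4 period runs to 21 July 2021 (28 July with the window), past the protocol date. Time needed for IRB approval of this version would shorten that overlap. No effect on the study's summaries has been shown. The case for correction rests on giving sites one instruction about a procedure that the sponsor treated as a safety matter.

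**What to change.** 1. Reconcile the Table 4 ABR row and footnote with Section 12.2.6 and Tables 5 and 6, so that one ABR instruction and one date appear throughout. The date wording should match too: Section 12.2.6 and Table 5 begin on 20 January 2021, while Table 6 says after it.
2. Clarify the footnote's last sentence, stating which evaluation and which time point it covers.
3. Have Sections 12.2.6.1 and 13 cite Tables 4, 5 and 6.

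What the single instruction should be is for the sponsor to settle. The cost is amendment wording, with no change to design, data collection forms or analysis.
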